5.2.1 Zone 2 Aneurysm Cohort

Primary analysis timing will be dependent only on those Subjects enrolled during Primary Enrollment. The Primary Endpoint for the Zone 2 aneurysm cohort will be analyzed after all available Subjects meeting the analysis population criteria have completed the 12 month followup visit and have been in the study through 546 days.

The subjects accrued during Continued Access Enrollment will be analyzed separately from the subjects accrued during Primary Enrollment at primary analysis. Depending on the timing of the primary analysis, continued access Subjects may not be analyzed at the time of primary analysis.

5.2.2 Zone 0/1 Aneurysm Cohort

The Primary Endpoint for the Zone 0/1 aneurysm cohort will be analyzed after all available Subjects meeting the analysis population criteria have completed the one month follow-up visit and have been in the study through 59 days. Subjects with suspected stroke Primary Endpoint events will need to have been in the study through 120 days before this Primary Endpoint analysis will be performed. This extra time is needed for these Subjects to allow for the Modified Rankin Scale to be assessed at any time during this period.

This analysis will also be repeated with 12 month results (following the same analysis population logic as that outlined for the Zone 2 aneurysm cohort in **Section 5.1.1.1**) with the exception that no hypothesis will be tested.

5.2.3 NAL Cohorts

The Primary Endpoint for each of the NAL cohorts will be analyzed at the same time as the Zonerespective aneurysm cohort (i.e. Zone 2 NAL cohorts will have primary analysis conducted when the Zone 2 aneurysm cohort has primary analysis conducted). This analysis may be repeated for each of the NAL cohorts at later timepoint(s). This will possibly be conducted at different times for each of the NAL cohorts.

No hypotheses will be tested on the NAL cohorts.

GORE CONFIDENTIAL INFORMATION

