5.1 Analysis Populations

- 5.1.1 Primary Endpoint
 - 5.1.1.1 Zone 2 Aneurysm Cohort

The composite Primary Endpoint analysis population (to test the hypothesis) for the Zone 2 aneurysm cohort will be among enrolled Subjects (excluding those with a CEC adjudicated 'major' inclusion/exclusion criteria violation or FDA mandated exclusion) and is outlined as follows based on events described in **Section 2.3.1.1**:

- 1) Subjects with an event any time ≤ 546 days are a failure regardless of whether they had imaging in 12 month window
- Subjects that don't have imaging in the 12 month window and don't have an event ≤ 546 days are excluded
- Subjects with imaging in 12 month window and no event reported ≤ 546 days are successes
- 4) Subjects with >1 event just count once as failures

The rate (composite Primary Endpoint) within an analysis window (except for Procedure window) will use similar logic to that through 12 month window but will be window-dependent (i.e. 6 Month Primary Endpoint composite rate will be among those with an event in the 6 month window or had imaging in the 6 month window). All enrolled Subjects with no 'major' inclusion/exclusion criteria will be in the denominator in the Procedure window.

GORE CONFIDENTIAL INFORMATION

All hypothesis testing and Primary Analysis for the PMA will be based on Zone 2 Aneurysm Subjects accrued during the Primary Enrollment Period. Zone 2 Aneurysm Subjects accrued during Continued Access Enrollment will be analyzed separately for the PMA. Continued Access Enrollment Subjects may be pooled with the Primary Enrollment Subjects in subsequent reports and/or analysis.

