5.1.1.3 NAL Cohorts

[figure not shown]
No hypotheses will be tested for any of the NAL cohorts. An NAL cohort will be summarized separately if there are at least 10 Subjects for a cohort. Else, NAL Subjects may be grouped by Zone (Zone 0/1, Zone 2) for analysis instead.

The Primary Endpoint analysis population for each of the five NAL cohorts will be among all enrolled Subjects (excluding those with a CEC adjudicated 'major' inclusion/exclusion criteria violation or FDA mandated exclusion). In addition, the Primary Endpoint analysis population for each NAL cohort will follow Zonesimilar logic to that written for the two hypothesis-driven aneurysm test arms (as described above in Section 5.1.1.1 (Zone 2) and Section 5.1.1.2 (Zone 0/1)).

[figure not shown]

GORE CONFIDENTIAL INFORMATION

However, additional analysis may be done with different analysis population criteria.

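### The first Zone 2 non-aneurysm (NAL) composite has no follow-up maturity condition, so it can be biased, usually downward, if NAL enrollment runs into the 546 days before data cutoff

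*SAP*

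**What the plan says.** **Timing.** SAP 5.2.3 ties NAL timing to the aneurysm arm of the same zone: "The Primary Endpoint for each of the NAL cohorts will be analyzed at the same time as the Zonerespective aneurysm cohort". It makes a later repeat optional and adds "No hypotheses will be tested on the NAL cohorts". The aneurysm arms do have a waiting condition. Under SAP 5.2.1, available Zone 2 subjects must "have completed the 12 month followup visit and have been in the study through 546 days". Under 5.2.2, Zone 0/1 subjects must "have completed the one month follow-up visit and have been in the study through 59 days", with 120 days for suspected strokes. For Zone 2, "Primary analysis timing will be dependent only on those Subjects enrolled during Primary Enrollment".

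**Denominator.** SAP 5.1.1.3: "the Primary Endpoint analysis population for each NAL cohort will follow Zonesimilar logic to that written for the two hypothesis-driven aneurysm test arms". For Zone 2 that is the rule in 5.1.1.1. Any event up to day 546 is a failure, with or without imaging. Imaging in the 12-month window with no event is a success. For the remainder, "Subjects that don't have imaging in the 12 month window and don't have an event ≤ 546 days are excluded". SAP Table 3 puts the 12-month analysis window at days 243-546.

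**The concern.** The denominator rule is reasonable only once every subject has had time to be imaged and to reach day 546. For the aneurysm arms the timing sections secure that. The NAL cohorts take over the rule without the wait, and their cutoff is set by other subjects.

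Consider a Zone 2 NAL subject treated four months before cutoff. A disabling stroke on day 2 puts that subject in the denominator as a failure. Without an event, the subject drops out of the rate, because a 12-month scan is not yet possible. That is not missed imaging: the favorable outcome cannot yet be observed.

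At stake is the descriptive purpose in SAP 2.1.1, which is to characterize performance in non-aneurysm lesions. A rate that shifts with recency of enrollment is hard to compare across NAL cohorts or with the Zone 2 aneurysm cohort. Continued Access subjects face the same problem if they are analyzed at the primary analysis, since they do not set its date either.

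**Working it through.** **Nearest stated figure.** The plan gives no expected NAL rate. SAP 2.4.1.1 gives historical Zone 2 aneurysm success of 81% with a 95% lower bound of 71%, n = 75. Check: 61/75 = 81.3%, and the two-sided exact lower bound is 70.7%, which rounds to 71%. I use 81% as one assumed true NAL rate. The second is 81 - 6 = 75%, taking the midpoint of the 5-7% technical-success loss that the 81% omits.

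**What the rule does, by follow-up at cutoff (Zone 2)**

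| Follow-up | Event | Event-free, imaged in window | Event-free, not imaged in window |
|---|---|---|---|
| under 243 days | failure | impossible | excluded |
| 243 to 545 days | failure | success, although events still count to day 546 | excluded |
| 546 days or more | failure | success | excluded (imaging truly missed) |

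The first row pushes the rate down. The second pushes both ways: subjects not yet scanned drop out, while scanned subjects are credited early.

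**Simple case.** Let p be true success, q = 1 - p, w the share of subjects with under 243 days, and e the share of all failures that have already occurred in them. Everyone else is mature.

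Reported rate = p(1 - w) / [(1 - w) + q·e·w]

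With p = 0.81, w = 0.2, e = 0.6: 0.648 / (0.8 + 0.0228) = 78.8%.

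Small cohorts move more. Six mature subjects with five successes give 5/6 = 83%. Add four recent subjects, one with an early event, and the rate is 5/7 = 71%; the other three vanish.

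**Accrual scenarios.** The following are assumptions, not in the documents:
- NAL accrual is uniform.
- 12-month imaging is spread evenly over days 243-455.
- A share e of failures (40-80%) falls evenly in days 0-30 and the rest evenly to day 546.
- Aneurysm accrual takes 730 days (the Protocol Summary says 18-24 months), so cutoff is day 730 + 546 = 1276.

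For follow-up f:
- F(f) = q·e·f/30 to day 30, then q[e + (1 - e)(f - 30)/516] to day 546, then q.
- G(f) = 0 below day 243, (f - 243)/212 to day 455, then 1.
- Reported rate = mean[G(1 - F)] / (mean[G(1 - F)] + mean[F]).

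| NAL accrual | Follow-up at cutoff (days) | Share under 243 days | Reported, true 81% | Reported, true 75% |
|---|---|---|---|---|
| Closes with aneurysm Primary Enrollment | 546-1276 | 0% | 81% | 75% |
| Closes 365 days later | 181-1276 | 6% | 78.7-79.6% | 72.3-73.4% |
| Runs to cutoff | 0-1276 | 19% | 76.7-78.4% | 69.8-71.9% |
| Only in last 546 days | 0-546 | 45% | 64.0-70.2% | 55.7-62.6% |

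Ranges are over e. Example for the third row, p = 0.75, e = 0.6: 0.5481 / (0.5481 + 0.2257) = 70.8%. The third row is 81 - 78.4 = 2.6 to 75 - 69.8 = 5.2 points low. The fourth is 81 - 70.2 = 10.8 to 75 - 55.7 = 19.3 points low.

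**Upward case.** If every subject has 455-476 days, all are imaged. At the midpoint, day 465.5, F = q[e + (1 - e)(435.5/516)]. With p = 0.75, e = 0.6: 0.25(0.6 + 0.4 × 0.844) = 0.234. The reported rate is 76.6%, 1.6 points high. With follow-up spread over 400-546 days and e = 0.6, the excess is 0.3-0.5 point.

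**Zone 0/1 at one month.** The window is days 15-59 (SAP Table 4). Assume true success of 75% or 65%, 80% of failures spread over days 0-30, imaging on days 23-44, and accrual to cutoff. The rate is then at most 0.7 point low with one year of accrual and under 0.2 point low with 48-60 months.

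**The case against.** The strongest reply has four parts, and much of it stands.

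- **The bias is conditional.** A reader might infer that the reported rate is too low. The documents do not support that as a fact. They state no NAL accrual period or closing date, and if NAL accrual stopped with aneurysm Primary Enrollment, every NAL subject has 546 days and there is no bias. Equally, nothing visible requires that closure.
- **Immature subjects do not all enter as failures.** A reader might infer that they do up to day 546. That is exact only below day 243. After that, imaged event-free subjects enter as successes, which offsets part of the bias and can reverse it.
- **Large figures need special accrual.** A reader might expect a deficit above ten points as routine. Uniform accrual to cutoff gives about 3-5 points and puts only 365/1276 = 29% of subjects in the last year. Double-digit bias needs NAL accrual that starts late or accelerates, which no section indicates.
- **The NAL arms are descriptive.** They have no hypothesis or performance goal, so no pass/fail result changes. The main error also makes the device look worse.

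The plan offers partial cover: an optional repeat (5.2.3), optional other populations (5.1.1.3), serial and final analyses (5.2), and Kaplan-Meier analysis of mortality and reintervention (5.5.6, 5.5.7). None of these makes the first NAL composite mature. The sensitivity analyses mentioned in 5.3.1 address the hypothesis tests, which the NAL arms lack.

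**Conclusion.** The gap is real. For Zone 2 NAL, the written rule combines immediate counting of failures, delayed counting of successes, and a cutoff that ignores NAL follow-up. The resulting error in the first reported rate ranges from none to 11-19 points low, with 3-5 points low for uniform accrual to cutoff and a point or two high in a narrow pattern. Which applies depends on NAL accrual dates that the documents do not give. The sizes also rest on the assumed true rate, event timing and scan timing. The row-by-row effect of the rule does not.

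This is a moderate point about descriptive results. The aneurysm hypothesis tests are untouched, and Zone 0/1 at one month needs only a consistent rule.

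**What to change.** - **Zone 2 NAL (5.1.1.3 and 5.2.3).** At each analysis, include only subjects whose index procedure was at least 546 days before data cutoff, whether or not they had an event. Report how many are not yet mature and list their events. Make the repeat mandatory once all NAL subjects are mature. Under the assumptions above with complete imaging, the expected rate returns to 81% or 75%.
- **Continued Access (5.2.1).** Apply the same filter if these subjects are analyzed at the primary analysis.
- **Zone 0/1 NAL, and the Zone 0/1 12-month repeat (5.2.2).** Use one clock for treated and never-treated subjects, for example the Phase 1 date plus the 60-day staging allowance plus 59 days (119 days), or plus 546 days (606 days) for the 12-month repeat. Starting the clock at Phase 1 for never-treated subjects and at the index procedure for treated ones would admit failures up to 60 days sooner and recreate the problem. Keep the 120-day condition for suspected strokes as a condition on when the analysis is run.

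The cost is SAP wording and a date filter. The first reported rate will rest on fewer NAL subjects, and early events in immature subjects will appear in a listing instead of the rate. A censored time-to-event estimate could be added to use all subjects.

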5.3 Primary Endpoint Analysis

5.3.1 Zone 2 and Zone 0/1 Aneurysm Cohorts

The proportion of composite Primary Endpoint success (1 - composite Primary Endpoint failure) will be calculated for each hypothesis-driven cohort based on the details outlined for each Primary Endpoint component in **Appendix A**. One-sided Exact confidence intervals for binomial proportions (alpha=0.05) will be constructed to test each calculated composite proportion against the respective Primary Endpoint hypothesis. Each hypothesis-driven cohort tested must meet their respective Primary Endpoint analysis population criteria. The null hypothesis will be rejected if the lower bound of the 95% confidence interval estimating composite Primary Endpoint success exceeds the performance goal.

In addition, the Primary Endpoint data (composite and components) for each of these two cohorts will be summarized by statistics (count and percent).

In order to assess the impact of missing data on each of the composite Primary Endpoint hypothesis tests, sensitivity analyses will be performed and are outlined in **Section 5.5.1**.

5.3.2 NAL Cohorts

The Primary Endpoint data (composite and components) for the five cohorts meeting their respective Primary Endpoint analysis population criteria will be summarized by descriptive statistics (count and percent). No hypotheses will be tested.

5.5 Additional Analyses

Additional analyses will be performed as outlined below.

GORE CONFIDENTIAL INFORMATION

5.5.3 Poolability of Sites

Site data will be pooled based on clinical comparability, i.e., the study Sites followed a common protocol, the study was monitored to ensure compliance with the protocol and applicable government regulations, and the data collection and handling procedures were the same at all study Sites. In order to justify pooling of Sites, a 2 x k analysis of the composite Primary Endpoint results (separately for the Zone 2 aneurysm and Zone 0/1 aneurysm cohorts) using a generalized Fisher's exact test will be performed, where k represents the number of site groups. Sites may be grouped together based on low enrollment with consideration given to the overall percent of enrollment combined. A 0.15 level of significance will be used for each test between site group and composite endpoint result. If the test is significant, composite Primary Endpoint results with 95% confidence intervals will be presented by Site group for each of the hypothesis-driven cohorts (Zone 2 aneurysm, Zone 0/1 aneurysm).

5.5.4 Adverse Events

Adverse events (AEs) will be summarized for main reporting efforts. Adverse events are defined as any untoward medical occurrences in a Subject whether device-related or not. All AEs will be recorded on the appropriate CRF and documented in the Subject's permanent medical record. The Investigator at each Site is ultimately responsible for reporting all AEs to the Sponsor, as well as to the IRB, as applicable.

Adverse events will be summarized by incidence (i.e. a specific AE will not be counted more than once for a Subject within each window) in each analysis time window using MedDRA coded terminology. Analysis time windows will begin with the initial endovascular treatment window for all cohorts; AEs with onset prior to endovascular treatment (Zone 0/1 cohorts only) will be summarized separately. The denominator for each window will be calculated as the number of Subjects remaining in follow-up as of the beginning of the analysis window. At a minimum, separate summaries by severity (serious, non-serious) will be prepared. If summaries are prepared by relationship, the following categories will be considered as related to device/procedure: related to device, related to device and endovascular procedure, or related to endovascular procedure.

Partial dates (month and/or day unknown) for AE onset and AE resolution dates will be allowed for AE analysis time window determination. Exact imputation logic will be documented in the appropriate specifications document. In general, partial dates will be imputed to be most conservative with regard to timing after initial endovascular procedure date.

Candidate AEs for Primary Endpoint and Success Outcomes will be reviewed by the independent CEC and adjudicated (outlined in Appendix A).

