5.1.3 Additional Analyses

The analysis population for all other analyses (outlined in **Section 5.5**) for each of the cohorts will be among enrolled Subjects (excluding those with a CEC adjudicated 'major' inclusion/exclusion criteria violation or FDA mandated exclusion). Any additional analysis population details are outlined in the appropriate subsection of **Section 5.5**.

5.2 **Timing of Analyses**

Prior to primary analysis, the composite Primary Endpoint results

will not be analyzed (except as detailed below in Section 5.2.2) for the two hypothesis-driven test arms. Serial analyses of long-term results will occur during the follow-up period. A final analysis will be conducted once study follow-up is complete. In addition to the Primary Endpoint at primary analysis time points, all other additional analyses (detailed in Section 5.5) will also be performed.

Details on primary analysis timing are provided in the below subsequent sections:

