5.5.7 Reinterventions

A Site-reported reintervention will be counted as occurring if the Site reports a 'yes' to the question "Was reintervention on the treated segment of the branch vessel or the aorta performed?" from the AE CRF. The incidence of Site-reported reinterventions will be summarized by analysis time window among those remaining in follow-up. In addition, the time to first Site-reported reintervention will be calculated using Kaplan Meier methodology. Subjects without a Site-reported reintervention reported before the end of the time period of interest will be censored at the Subject's last reported contact date or the end of the time period of interest, whichever date is earlier.

Unanticipated additional procedures related to the device, procedure, or withdrawal of the delivery system (meeting Primary Endpoint or Success Outcome criteria) will be summarized in the Primary Endpoint and Success Outcome tables and are not reconciled with Site-reported reinterventions as described above.

Initially treated Zone 2 cohort Subjects that have a reported reintervention involving Zone 0/1 treatment will remain in their original enrolled cohort for statistical analysis but narratives will be provided on these Subjects in submissions to the FDA (in all appropriate sections of the submitted report). In addition, the number and percent of these Subjects will be summarized.

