6.0 Interim Analyses and Safety Monitoring Analyses

There are no planned interim analyses of composite Primary Endpoint results for the two hypothesis-driven test arms.

However, safety data will be periodically reviewed by the DSMB (see **Section 4.4**). A comprehensive summary of reported adverse events will be reviewed by the DSMB on a regular and ongoing basis throughout the duration of the study. Safety data may be presented in various ways, such as serious adverse events vs. non-serious adverse events. In addition, adverse events resulting in mortality and/or in site-reported reinterventions may be presented separately.

Serial analyses of long-term results will occur during the follow up period.

GORE CONFIDENTIAL INFORMATION

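### Adverse event incidence is diluted in any window still open at a data cut, because the denominator is everyone who entered the window

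*SAP*

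**What the plan says.** **Denominator and numerator.** SAP Section 5.5.4 states: "The denominator for each window will be calculated as the number of Subjects remaining in follow-up as of the beginning of the analysis window". The numerator is an incidence count: "a specific AE will not be counted more than once for a Subject within each window". No person-time or Kaplan-Meier AE rate is described.

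**Windows.** SAP Tables 3 and 4 have a column of windows specifically for adverse events. After month 12 each is about a year long: days 366-731, 732-1096, 1097-1461 and 1462-1826.

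**Timing.** Section 5.2 has all Section 5.5 analyses performed at the primary analysis, and adds "Serial analyses of long-term results will occur during the follow-up period". Section 6.0 repeats this. The Zone 2 primary analysis waits until subjects "have been in the study through 546 days" (Section 5.2.1). The Zone 0/1 analysis waits for day 59, or day 120 for subjects with a suspected stroke (Section 5.2.2). A final analysis follows once follow-up is complete.

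**Reinterventions.** Section 5.5.7 states: "The incidence of Site-reported reinterventions will be summarized by analysis time window among those remaining in follow-up". It gives no time point at which this is judged. It also plans that "the time to first Site-reported reintervention will be calculated using Kaplan Meier methodology", and subjects without a reintervention "will be censored at the Subject's last reported contact date or the end of the time period of interest, whichever date is earlier".

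**The concern.** The rule works when every subject in the denominator has had the whole window in which to show an event. It fails when the cut falls inside the window. Day 546, the Zone 2 trigger, lies inside the window of days 366-731, and subjects enrolled earlier are by then in later windows. The numerator holds only events recorded so far, while the denominator counts each of these subjects as fully observed.

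The shortfall grows with the lateness of the window, because later windows are less mature at any given cut. A device with a constant event rate would therefore appear to have a falling one. The tables at stake are the AE summaries, including those by seriousness and by relationship to device or procedure, for an implant followed for five years.

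Other parts of the SAP guard against this. The within-window primary endpoint rates require an event or imaging in the window (Section 5.1.1.1), the Core Lab rates require a finding in the window (Section 5.5.5), and mortality is analysed with censoring (Section 5.5.6). The AE tables have no such guard.

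**Working it through.** The plan states no AE rate, so there is no figure to reproduce. The check asks what fraction of a window has been observed, on average, among subjects who have entered it.

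**Inputs from the documents**
- AE windows: SAP Tables 3 and 4.
- Minimum follow-up at the primary analysis: 546 days for Zone 2, 59 days for Zone 0/1 (SAP Sections 5.2.1 and 5.2.2).
- Aneurysm accrual: 18-24 months for Zone 2, 48-60 months for Zone 0/1 (Protocol Summary).

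**Assumptions not in the documents**
- Uniform accrual.
- Constant event rate within a window.
- No dropout or death.
- A cut on the day the last subject reaches the minimum follow-up.
- Every entered window is tabulated.

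**Formula.** Follow-up at the cut, F, is uniform from m to m + A, where m is the minimum follow-up and A the accrual period. For a window from day s to day e, a subject enters if F ≥ s and has observed the fraction min(1, (F − s)/(e − s)). The ratio of tabulated to true rate is approximately the mean of this fraction among those who entered.

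**Zone 2, 24-month accrual** (F from 546 to 546 + 730 = 1276)
- Days 366-731: all have entered. Finished: (1276 − 731)/730 = 0.747. The other 0.253 have mean F = 638.5, so have observed (638.5 − 366)/365 = 0.747. Ratio: 0.747 + 0.253 × 0.747 = **0.94**.
- Days 732-1096: entered (1276 − 732)/730 = 0.745. Of these, finished (1276 − 1096)/544 = 0.331; the other 0.669 have observed half on average. Ratio: 0.331 + 0.669 × 0.5 = **0.67**.
- Days 1097-1461: entered (1276 − 1097)/730 = 0.245, about 21 of 85. None has finished. Ratio: (179/2)/364 = **0.25**.

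**Zone 2, 18-month accrual** (F from 546 to 546 + 548 = 1094)
- Days 366-731: finished (1094 − 731)/548 = 0.662. Ratio: 0.662 + 0.338 × 0.747 = **0.91**.
- Days 732-1096: entered (1094 − 732)/548 = 0.661, none finished. Ratio: (362/2)/364 = **0.50**.
- Days 1097-1461: nobody has entered, because 1094 < 1097.

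In both cases the 1-, 6- and 12-month windows are complete and the ratio is 1.00.

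**As rates.** Take a true full-window risk of 10% and average 1 − 0.9^(fraction observed). The tables would show 9.2-9.4%, then 5.1-6.7%, then 2.6% (24-month accrual only). True risks of 5% and 20% give almost the same ratios.

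**Zone 0/1, cut at day 59.** The same formula with 48-60 months of accrual (1461-1826 days) gives:

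| AE window | Mean fraction observed, 48-60 months of accrual |
|---|---|
| 1 month | 1.00 |
| 6 months | 0.97 |
| 12 months | 0.93-0.95 |
| 24 months | 0.84-0.88 |
| 36 months | 0.77-0.84 |
| 48 months | 0.57-0.77 |
| 60 months | 0.08-0.57 |

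The lowest value is the 60-month window with 48-month accrual. F reaches 59 + 1461 = 1520, so only (1520 − 1462)/1461 = 4% have entered, and the fraction is (58/2)/364 = 0.08.

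**Later cuts.** For an illustrative Zone 2 cut with the last subject at day 911 and a true risk of 10%, the ratio is 1.00 through the 24-month window. It is 0.92-0.94 at 36 months, 0.51-0.67 at 48, and 0.26 at 60 (24-month accrual only). At the final analysis it is 1.00 throughout.

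**The case against.** **Scope.** A reader might infer that all late-window rates are too low at every serial analysis. The documents do not support that. The dilution arises only in windows that some subjects have entered but not had time to finish at that cut. Each later cut closes more windows, and the final analysis has none open.

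**Reinterventions.** A reader might also carry the AE denominator over to reinterventions. Section 5.5.7 does not say that follow-up status is judged at the start of the window, and its Kaplan-Meier analysis already handles partly observed time. Only the by-window reintervention table is in question, and there the defect is an undefined time point.

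**Size.** The Zone 2 24-month window, which every subject has entered, is only 6-9% low. The 25% figure needs 24-month accrual and concerns about a quarter of subjects. All the figures depend on the assumed accrual pattern and on open windows being tabulated.

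**Text not seen.** The SAP contents list Sections 7.1 and 7.2 on dataset and output specifications, but the available text does not reproduce them, nor the list of tables in Section 8.1. A rule on data cuts or display could stand there. This limits certainty that open windows will be shown. It does not change Section 5.5.4, which states its denominator outright.

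**Consequence.** These tables are descriptive, and neither hypothesis test uses this denominator.

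All of these limits stand. None removes the bias in the open windows.

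**Conclusion.** The point holds for AE incidence in windows still open at a data cut. The bias is downward. At the Zone 2 primary analysis it is slight for days 366-731 (ratio 0.91-0.94), substantial for days 732-1096 (0.50-0.67), and severe for the few subjects in days 1097-1461 (about 0.25, 24-month accrual only). Zone 0/1 has open windows from 6 months on. These sizes rest on the assumptions listed with the calculation; the direction does not depend on uniform accrual.

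Windows that every subject has had time to complete, the final analysis, both hypothesis tests, and the Kaplan-Meier analyses of mortality and reintervention are not affected by the data cut. The sponsor should make the change, because the bias is predictable and can make a constant event rate look like a declining one. It does not threaten the primary conclusions.

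**What to change.** In Section 5.5.4, at each data cut, take as the denominator for a window the subjects who meet both conditions:
1. they were in follow-up at the start of the window; and
2. their index procedure was at least (window end) days before the cutoff.

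Keep those who died or withdrew during the window, and count events in the same subjects. Both conditions are needed. The second alone would bring in subjects who had left before the window opened and could not contribute events. Requiring actual completion of the window would drop those who died in it.

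For windows not yet matured, report events per subject-year observed, or a Kaplan-Meier estimate, and label the window incomplete.

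Apply the same rule to the by-window reintervention table in Section 5.5.7, and state there when follow-up status is judged. The Kaplan-Meier analysis in that section stays as planned.

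Under the assumptions used here, the expected rate in a matured window is then the true rate. The cost is a few sentences in the SAP, a small programming change, and fewer subjects shown in late windows until they mature.
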